3.4 Endpoints/Outcomes Measurements

Hypothesis: Interfacing with primary care practices to encourage physicians to implement default online orders of blood glucose flowsheets and informational messaging for all patients with diabetes will increase patient adoption.

Outcome Measures: Comparison of individuals between treatment and control practices-- (a) fraction of patients entering blood glucose measurements into MyChart flowsheets during implementation period & follow-up period (dichotomous), (b) mean number of flowsheet entries during implementation period and follow-up period (c) fraction of patients for whom order is placed by doctor

Hypothesis: Additional reminder messaging to patients that (1) emphasizes the value of tracking blood glucose data to the patient OR (2) emphasize the value of tracking blood glucose data to the doctor OR (3) informs patient of their selection for a chance to receive an award conditional on tracking will increase adoption relative to no reminder messaging.

Outcome Measure: Comparison of individuals across reminder messaging assignment groups (within treatment practices)-- (a) fraction of patients entering blood glucose measurements into MyChart flowsheets during implementation period & follow-up period (dichotomous), (b) mean number of flowsheet entries during implementation period and follow-up period

Hypothesis: Promotion of adoption of electronic blood glucose tracking through the means described above will result in the following intent-to-treat effects:

(a) reduction in patient A1c

Outcome Measures: Intent to treat comparison of individuals between treatment and control practices of the following measures at the end of the intervention period and follow-up period: (1) Mean A1c (2) Quartiles of A1c using quantile regression analysis (3) fraction of patients experiencing improvement [reduction] in A1c from baseline (dichotomous) (4) fraction of patients below benchmark 7.0% A1c (dichotomous)

(b) increase in frequency of doctor-patient interaction

Outcome Measures: Intent to treat comparison of individuals between treatment and control practices of the following measures during the intervention period and follow-up period: (1) number of securing messaging (2) number of phone interactions, and (3) number of in-office appointments

(c) changes to treatment plan path

Outcome Measure: Intent to treat comparison of individuals between treatment and control practices of number of alterations to patient prescriptions/medication list during the intervention period and follow-up period

Hypothesis: Reminder messaging treatments that induce more intensive use of flowsheets will lead patients to experience larger effects as described above.

Outcome Measure: Intent to treat and treatment on the treated comparison of individuals across reminder messaging assignment groups (within treatment practices)-- reduction in A1c, increase in frequency of doctor-patient interactions, changes to treatment plan path (outcomes as described above in a-c)

Hypothesis: Entries of blood glucose data will be predictive of A1c and will lower over the study period.

Outcome Measure: Descriptive analysis of flowsheet entry values in the treatment group during the implementation and follow-up period.

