1.1 Specific Aims

This study aims to test methods of increasing adoption and integration of blood glucose monitoring into electronic medical records, and to measure the impact of widespread adoption on health status of patients with diabetes. To investigate determinants of adoption, the research will combine and test doctor and patient focused approaches to encouraging patient use of blood glucose flow sheets through the online patient portal, MyChart. Adoption will be measured on both the extensive and intensive margin: the number of patients who enter data into the flowsheets at all during the study period, and the mean number of entries per patient during the study period. Conditional on statistically significant increases in adoption, the study will examine corresponding intent-to-treat effects on patient health, and consider possible mechanisms through which health indicators improve or do not improve.

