1.2 Hypotheses

1.2.1 Interfacing with primary care practices to encourage physicians to implement default online orders of blood glucose flowsheets and informational messaging for all patients with diabetes will increase patient adoption (as defined above).

1.2.2. Additional reminder messaging to patients that (1) emphasizes the value of tracking blood glucose data to the patient OR (2) emphasize the value of tracking blood glucose data to the doctor OR (3) informs patient of their selection for a chance to receive an award conditional on tracking will increase adoption relative to no reminder messaging.

1.2.3 Promotion of adoption of electronic blood glucose tracking through the means described above will result in the following intent-to-treat effects:

- (a) reduction in patient A1c
- (b) increases in frequency of doctor-patient interaction
- (c) changes to treatment plan path

1.2.4 Reminder messaging treatments that induce more intensive use of flowsheets will lead patients to experience larger effects as described in 1.2.3.

1.2.5 Entries of blood glucose data will be predictive of A1c on average and will lower over the study period.

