Inova patients can track their blood glucose electronically through MyChart, allowing physicians to view their data in real time and be notified if results are out of range. More recently, functionality has been developed to connect Apple's HealthKit to MyChart, such that patients with compatible glucometers can link them to their smartphones, which can in turn be linked to MyChart to automatically transfer glucometer readings to the EHR. This update streamlines the tracking process for patients with compatible devices. Despite these capabilities however, few doctors and patients at Inova use MyChart's blood glucose flowsheets. In order for patients to use the flowsheets, their physician must place an order through the EMR, and this initial step is rarely taken.

Recent research suggests that informational frictions are a key barrier to updating convention across medical practices (Chan 2016). Anecdotal evidence supports that many physicians at Inova are not aware of blood glucose tracking features in MyChart or how to set up tracking. This study will seek to test an intervention to inform physicians of the tracking capabilities, and give guidance for placing bulk glucose flowsheet orders for all patients with diabetes. This aspect of the intervention is intended to remove barriers to physician action, setting a default such that patients have access to the tracking feature.

However, SMBG is most effective when patients track regularly. Many of the studies discussed above show a correlation between adherence and reduction in A1c. This study will also test the effect of reminder messaging on patient use of the flowsheets. One version of messaging will emphasize physician engagement and monitoring of flowsheet entries. Previous research has shown doctor patient communication is predictive of adherence (Friedman et al 2008). Patients may feel more accountability and value to tracking if they anticipate their physicians will be looking at their results. Additionally, as part of this design, some patients will be given a chance to receive a gift card if they fill out the flowsheets, intended to provide compensation for time spent setting up and learning how to use the

tracking features. Past research in other contexts has shown higher adherence to patient driven behaviors when such compensation is provided (Roski et al 2003).

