3.1 Study Treatment/Intervention

The focus of the study treatment will be to encourage adoption of the blood glucose monitoring feature of MyChart by patients with diabetes and their providers. Currently, providers must place an order to allow patients to enter their blood glucose into the online system. If patients enter data, providers are then able to view these readings through the patient portal. This feature is currently available, but awareness and utilization are low. The sections describe intervention design, which will promote adoption.

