3.1.1 PRACTICE LEVEL PROMOTION

Providers in the randomly selected group of treatment primary care practices will be encouraged to batch order blood glucose flowsheets for all patients with diabetes with active MyChart accounts. The research team will contact physicians and practice managers with an explanation of the initiative and instructions for completing batch orders and viewing entries through the system. The practice will be advised to complete filling orders over a two week administration period, after which the implementation period will begin. A batch order will trigger two forms of alerts sent to providers, according to the default settings for electronic glucose flowsheets:

1. A bi-weekly report received of values that the patient has entered, or a notification that the patient has not entered data during the interval.
2. A notification when patient entered values are out of range (the patient also gets a notification that their doctor will see this value) according to the following current settings:

Notification Setting	Current Default
Pre-Meal Range (entry outside range=alert)	60-180 mg/dl
Post-Meal Range	100-240 mg/dl
Nighttime Range	60-300 mg/dl

Patients will automatically be notified when the flowsheet has been ordered for them. Additionally, providers will be given text for a secure smart-text message to send to all patients receiving the flowsheets, instructing them to enter data for the study period. The secure message will also provide them with information on how to enter data, and on the benefits of tracking blood glucose. Draft text of this message is included below:

Dear [Patient],

You may have seen that there is a new electronic form available for you to enter your blood glucose results in the MyChart portal. Keeping track of your blood glucose can help you manage your diabetes and reduce your chances for developing complications like heart disease, kidney damage and eye damage. As part of a new Inova program to help patients with diabetes get healthy, I would like you to try entering the results of your home blood glucose tests on MyChart for the next 3 months, through [Date]. Please let me know if you have any questions.

Sincerely,

[Practitioner]

WHAT TO DO NEXT

1. **Get help:** If you need help learning how to measure your blood glucose or getting testing supplies, you can contact [Practice Contact].

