3.1.2 INDIVIDUAL LEVEL REMINDERS

After the initial two-week roll-out/administration period, follow-up emails will be sent out by the research team to patients at treatment practices whose doctors have placed blood glucose flowsheet orders. Patients will be assigned at the individual level to one of four reminder treatment conditions, which will be administered by the research team. The number of reminder conditions may be reduced (to 2 or 3 instead of 4) depending on the rate of flowsheet orders by physicians to preserve statistical power. Assignment to any of these treatments will not preclude or provide guidelines for other communication between providers and patients (e.g. providers are free to send out their own reminders or messaging regardless of patient assignment to treatment group). The four reminder treatment conditions are described below:

(1) No additional reminders from research group

(2) Standard secure message reminder, addressed from Inova Medical Group, sent every two weeks during 12 week implementation period. Draft text below:

*Dear [Patient],
Don't forget to track your blood glucose through MyChart! Keeping track of your blood glucose can help you manage your diabetes and reduce your chances for developing complications like heart disease, kidney damage and eye damage.
Sincerely,
Inova Medical Group*

(3) Secure message reminder with chance to receive gift card, addressed from Inova, sent every two weeks during 12 week implementation period. Draft text below:

*Dear [Patient],
You have been chosen for a special program to help you get started tracking your blood glucose through MyChart. For each day that you track your blood glucose on MyChart through [DATE], you will be*

entered to receive one of fifty \$50 gift cards to Amazon. You'll be sent a secure message through MyChart after [DATE] if you've been selected to receive a gift card. Keeping track of your blood glucose can help you manage your diabetes and reduce your chances for developing complications like heart disease, kidney damage and eye damage.

Sincerely,

Inova Medical Group

(4) Secure message reminder, addressed from primary care doctor, sent every two weeks during 12 week implementation period. Draft text below:

Dear [Patient],

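### The adoption contrasts for hypothesis 1.2.1 measure promotion plus reminders, are not labelled as such, and no promotion-only estimate is specified

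*Combined protocol and SAP*

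**What the plan says.** Section 1.2 states hypothesis 1.2.1 as "Interfacing with primary care practices to encourage physicians to implement default online orders of blood glucose flowsheets and informational messaging", predicted to raise patient adoption. Hypothesis 1.2.2 is separate: further reminder messages "will increase adoption relative to no reminder messaging". Section 3.1.1 describes the informational message as a single provider text sent along with the flowsheet order.

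For 1.2.1, Section 3.4 gives "Comparison of individuals between treatment and control practices-- (a) fraction of patients entering blood glucose measurements into MyChart flowsheets during implementation period" and the follow-up period as outcome (a), the mean number of entries as (b), and orders placed as (c). For 1.2.2 it compares reminder groups inside treatment practices only.

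Under Section 3.1.2, "follow-up emails will be sent out by the research team to patients at treatment practices whose doctors have placed blood glucose flowsheet orders". There are four conditions: no reminder, and three fortnightly reminders, one of them with a gift-card chance. The number may be cut to three or two, depending on how many orders are placed. Section 3.2 gives control practices no encouragement. Section 3.3 assigns reminders by the first two letters of the surname. Section 4.2 lists no reminder term among the covariates.

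**The concern.** The hypothesis names one intervention and the contrast measures two. The reminders run during the implementation period, which lies inside the outcome window for (a) and (b), and they reach treatment-practice patients only. Any adoption they produce is therefore credited to practice promotion.

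No section compares the no-reminder condition with control practices, so the plan specifies no estimate of the effect that 1.2.1 describes. What the pooled contrast measures is also not fixed in advance, because the reminded share changes if conditions are dropped.

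The effect size is what matters here. A health system deciding whether to adopt outreach and default orders without recurring messages or gift cards needs the promotion-only figure.

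The point is limited to (a) and (b). Orders (c) precede the reminders. Hypothesis 1.2.3 refers to all the means of promotion together, so pooling is right there.

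**Working it through.** **Inputs.** From Section 4.1: 7,200 patients, 24 practices, control adoption 2%, ICC 0.1, stated MDE 9.5 points. For the reminder comparison: 3,600 patients, four arms, 20% adoption without reminders, stated MDE 5.5 points. Assumed because the plan does not state them: two-sided 5%, 80% power, 12 practices per arm of equal size (300 patients each).

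**Reproducing the plan's figures.** With m patients per practice and k practices per arm, the effective size per arm is n = k·m / [1 + (m − 1)·ICC]. The MDE d solves

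d = (t₀.₉₇₅ + t₀.₈₀) × √{[p₀(1 − p₀) + (p₀ + d)(1 − p₀ − d)] / n}, with 2k − 2 df.

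- Pooled contrast: n = 3,600 / (1 + 299 × 0.1) = 116.5; t quantiles 2.074 + 0.858; d = 9.45 points (plan: 9.5).
- Reminder contrast: 3,600 / 4 = 900 per group, from 20%, normal quantiles, no clustering; d = 5.53 points (plan: 5.5). This sizing implies four equal groups and full ordering, although Section 3.1.2 promises neither.

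**Size of the excess.** An order is a precondition for entry: "In order for patients to use the flowsheets, their physician must place an order through the EMR". So

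excess = order rate × reminded share × mean reminder effect.

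The 5.5 points below is the plan's MDE, used only as an illustration. The order rates below 100% are also illustrative.

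| Order rate | Reminded share | Mean effect (points) | Excess (points) |
|---|---|---|---|
| 100% | 3/4 (four conditions) | 5.5 | 4.1 |
| 100% | 2/3 (three) | 5.5 | 3.7 |
| 100% | 1/2 (two) | 5.5 | 2.75 |
| 50% | 3/4 | 5.5 | 2.1 |
| 25% | 3/4 | 5.5 | 1.0 |
| 100% | 3/4 | 0 / 2 / 10 | 0 / 1.5 / 7.5 |
| 100% | 0.6 to 0.9 (unequal surname groups) | 5.5 | 3.3 to 5.0 |

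If only one of three messages works by 5.5 points, the excess is 1/4 × 5.5 = 1.4 points at full ordering and 0.7 at 50%.

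**Relative to promotion alone.** Promotion alone = order rate × 20 − 2 points, taking no entries without an order. Four conditions, all three messages effective:

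- 100% ordering: 18.0 becomes 22.1 (4.125 / 18 = +23%)
- 50%: 8.0 becomes 10.1 (2.06 / 8 = +26%)
- 25%: 3.0 becomes 4.0 (1.03 / 3 = +34%)

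**Effect on power (ICC 0.1, 12 practices per arm).** At the plan's own rates (18 points), a promotion-only comparison with 75 patients per practice has about 98% power. At 50% ordering, 8.0 points has 66% power with 75 per practice (significance threshold about 6.6 points) and 70% with 300. The pooled 10.06 points has 83% with 300. Part of the gap between 66% and 83% is therefore sample size.

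**Precision of a promotion-only estimate.** MDE in points, one quarter of each practice in both arms:

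| ICC | Pooled, 300 v 300 | No-reminder groups, 75 v 75 | Increase |
|---|---|---|---|
| 0.1 | 9.45 | 10.03 | 6% |
| 0.05 | 5.94 | 6.66 | 12% |
| 0.02 | 3.44 | 4.32 | 26% |

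At ICC 0.1 it is 9.84 with three conditions (100 per practice) and 9.64 with two (150). With 10 practices per arm and 7,200 patients kept (360, then 90 per practice), the pooled and promotion-only MDEs are 10.90 and 11.47 at ICC 0.1, 6.79 and 7.49 at 0.05, and 3.86 and 4.72 at 0.02.

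**The case against.** The planned contrast is a valid intention-to-treat estimate of everything treatment practices receive. Section 3.1 places promotion and reminders under one study intervention, and Section 1.1 says "the research will combine and test doctor and patient focused approaches to encouraging patient use of blood glucose flow sheets". Reminders follow from an order, so they are a consequence of promotion and not a confounder. Hypothesis 1.2.1 is directional, and on the plan's rates its test is not at risk. A promotion-only figure can also be built from planned outputs: order fraction times adoption among ordered no-reminder patients, minus control adoption. Finally, the larger excess figures assume that all three messages work.

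Much of this stands. A package effect is a fair target, no reversal is shown, and the excess may be small or nil.

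Two things remain. Section 3.4 attaches the contrast to a hypothesis that names promotion only, whereas 1.2.3 shows how the plan words a combined effect. And the derivation is not specified; it would rest on the Section 3.3 assumption that surname grouping is unrelated to adoption. Matching on surname prefix avoids that assumption for the prefixes compared. It is still needed to extend the result to all surnames.

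**Conclusion.** The concern holds. Outcomes (a) and (b) under 1.2.1 estimate promotion plus reminders, and the result is too large as a promotion effect whenever hypothesis 1.2.2 is true. The missing label and missing estimate follow from the text alone.

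The size depends on unknowns. With the plan's 20% and 2%, four equal groups and full ordering, the excess runs from 0 to 7.5 points for mean reminder effects of 0 to 10 points, and is 4.1 points at 5.5. Lower ordering or fewer conditions shrinks it. This should be corrected before analysis. It does not invalidate the planned test or the stated 9.5-point MDE.

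**What to change.** - Keep the all-patient test for (a) and (b), and label it the effect of the full package (promotion plus reminders).
- Pre-specify one promotion-only estimate: treatment-practice patients in the no-reminder surname-prefix groups, whether or not an order was placed, against control-practice patients in the same prefix groups, with practice-clustered standard errors. Attribute an effect to promotion alone only from this estimate.
- A regression version needs prefix-group main effects, treatment, and treatment-by-prefix-group terms. Run it without the doctor fixed effects of Section 4.2, which absorb practice assignment if each doctor works in one practice.
- Carry a prefix-group code for every patient, controls included, and ask for it before the outcome queries are built.
- State the limits. The estimate is less precise, and extending it to all surnames needs the Section 3.3 assumption. Providers may send their own reminders. No-reminder patients share physicians with reminded ones (7,200 / 71 ≈ 101 patients per physician), whose entries trigger alerts and "A bi-weekly report received of values that the patient has entered".
- State the number of treatment practices. Section 6.2 implies 10; the 24 practices of Section 4.1, split equally, imply 12.

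Outcome (c) and the 1.2.3 contrasts stay as planned. The cost is SAP wording, one estimate and one data field. At the plan's ICC the added estimate's MDE is about 0.6 points above the pooled one, and the planned test loses nothing.

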2.3 Duration of Study

Primary care practices identified in the treatment group will be encouraged to place bulk orders for electronic glucose flowsheets over a period of two weeks. Patients will be actively encouraged to use flowsheets for 12 weeks following the administration period. Outcome data will be collected for a total of 38 weeks:

- (a) 12 weeks retrospective at baseline
- (b) 2 week administration period
- (c) 12 week implementation period
- (d) 12 week follow up period

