4.1 Sample Size

Non-pregnant adult patients of Inova primary care physicians with a current diabetes mellitus diagnosis and active MyChart account at time of treatment administration will be included in the study. The estimated number of patients is around 7200, from 71 primary care physicians across 24 selected Inova primary care practices.

Power Calculations

Power calculations were performed using the “clustersampsi” command in Stata. Knowledge of available sample and estimates/assumptions of control outcome mean, variance, and intraclass correlation were used to calculate a minimum detectable effect size for the key outcomes of flowsheet adoption (extensive margin, dichotomous rate of adoption) and changes in mean A1c.

Flowsheet Adoption: Practice Level Treatment-Control Comparison

Sample Size: 7200

Number of Treatment Arms: 2

Number of Clusters: 24

Assumed Control Adoption Rate: 2%

Assumed Intra-Cluster Correlation (within practices): 0.1

Minimum Detectable Effect: **9.5 percentage point increase in flowsheet orders**

Mean HbA1c: Practice Level Treatment Control Comparison

Sample Size: 7200

Number of Treatment Arms: 2

Number of Clusters: 24

Assumed Control HbA1c Mean: 6.74

Assumed Control HbA1c Standard Deviation: 1.39

Assumed Intra-Cluster Correlation (within practices): 0.07

Assumed Baseline Correlation: 0.80

ITT Minimum Detectable Effect: **0.27 change in A1c**

Flowsheet Adoption: Individual Level Comparison between Messaging Assignment Groups in Treatment Practices

Sample Size: 3600

Number of Arms (including no reminder): 4

Assumed No Reminder Adoption Rate: 20%

Minimum Detectable Effect: **5.5 percentage point increase in use of flowsheets when compared to no reminder**

Justification

The sample size represents the entire population of Inova primary care patients with diabetes who have active MyChart accounts and are therefore able to access the blood glucose tracking feature. The minimum detectable effects resulting from power calculations above are in-line with similar studies cited in the protocol background. Metastudy reviews of the effect of self monitoring of blood glucose found a 0.33 point change in A1c.

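### The practice-level adoption analysis counts patients who used the flowsheet before randomisation but does not adjust for that prior use, and the order outcome has no time window

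*Combined protocol and SAP*

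**What the plan says.** Section 1.1 defines adoption as any flowsheet entry in the study period, plus mean entries per patient. It makes the health analysis conditional on a statistically significant rise in adoption. For the practice-level comparison, Section 3.4 lists (a) the "fraction of patients entering blood glucose measurements into MyChart flowsheets during implementation period & follow-up period (dichotomous"), (b) mean number of entries over the same periods, and (c) the fraction of patients with an order, for which no period is given.

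Sections 2.5 and 4.1 admit adults with diabetes and an active MyChart account, with no condition on earlier flowsheet use or orders. Section 3.3 stratifies practices by number of diabetic patients only. The adjusted model in Section 4.2 uses age/gender, race/ethnicity, baseline A1c, days since the last visit, doctor fixed effects and a flag for another study. Baseline flowsheet use is not among them.

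The plan recognises that some use already exists. Section 1.3 says that "few doctors and patients at Inova use" the flowsheets, and the power calculation has "Assumed Control Adoption Rate: 2" per cent. Section 2.3 includes "12 weeks retrospective at baseline" in the outcome data to be collected.

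**The concern.** The first hypothesis is that outreach to practices increases adoption. A patient already entering values before randomisation will probably be counted under (a) in either arm, so that patient adds variation to (a) but little information about outreach. Use needs a physician's order (Section 1.3), and Section 4.1 counts only 71 physicians. Prior users may therefore be concentrated in a few practices, and where those practices fall by chance can shift the arm difference.

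Outcome (b) is probably the most exposed, because a regular user contributes many more entries than a patient who tries the feature once. For (c), counting every order on file brings old orders into both arms. Counting only new ones may miss treatment patients passed over in the batch because they already had an order. The plan does not say which is meant. Since the health analysis depends on the adoption result, avoidable noise here has consequences beyond the adoption outcomes themselves.

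**Working it through.** **Inputs.** From Section 4.1: "The estimated number of patients is around 7200, from 71 primary care physicians across 24 selected Inova primary care practices"; "Number of Clusters: 24"; "Assumed Intra-Cluster Correlation (within practices): 0.1"; control adoption 2%; stated MDE 9.5 points. Assumed, because not stated: 12 practices per arm, equal practice size (7,200/24 = 300, so 3,600 patients per arm), two-sided 5% test, 80% power.

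**Step 1: reproduce the stated MDE.** Design effect = 1 + (300 − 1) × 0.1 = 30.9. Effective n per arm = 3,600/30.9 = 116.5. Solve for d, with p1 = p0 + d:

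n·d² = (t(0.975; 22) + t(0.80; 22))² × [p0(1 − p0) + p1(1 − p1)]

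With p0 = 0.02 the solution is d = 0.0945. Check: (2.074 + 0.858)² = 8.60; 8.60 × (0.0196 + 0.1014)/116.5 = 0.00893; the square root is 0.0945. This rounds to the stated 9.5 points. Variants: 9.63 (t, pooled variance), 8.85 (normal, unpooled), 9.01 (normal, pooled).

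**Step 2: chance imbalance in prior users.** SE of the arm difference = √[2p(1 − p) × 30.9/3,600].

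| Prior-user prevalence p | SE (points) | 95% range (points) |
|---|---|---|
| 0.5% | 0.92 | ±1.8 |
| 1% | 1.30 | ±2.6 |
| 2% | 1.83 | ±3.6 |

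At 2%, the between-practice SD is √(0.1 × 0.02 × 0.98) = 4.4 points, and 4.4 × √(2/12) = 1.8, so nearly all of this is between-practice variation. These are the same 2% and ICC that entered Step 1. The 1.8 points are therefore already part of the 9.5, not an addition to it.

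**Step 3: how much could be removed.** The share of the 2% who are prior users is not given, so it is varied. Step 1 is repeated with the control rate that remains after removing them, holding the ICC at 0.1. Power for a 9.5-point increase uses the normal approximation.

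| Control rate left | Share of the 2% removed | MDE (points) | Power for +9.5 |
|---|---|---|---|
| 2% | none | 9.45 | 0.83 |
| 1% | half | 8.36 | 0.88 |
| 0.5% | three quarters | 7.69 | 0.91 |
| 0.05% | nearly all | 6.96 | 0.93 |

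For a 9.5-point effect, SE = √{[p0(1 − p0) + p1(1 − p1)]/116.5}. It falls from 3.23 points (p0 = 2%) to 2.99 (1%) and 2.72 (0%). A covariate explains prior use imperfectly, so these figures bound the gain from adjustment.

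**Step 4: mean entries.** The documents give no variance and no MDE for (b), so only the direction can be shown. Assume a prior user enters 6 values a week for the 24 weeks of implementation and follow-up: 6 × 24 = 144. Ten such patients in one arm add 1,440/3,600 = 0.4 entries per patient; sixty add 8,640/3,600 = 2.4. Sixty in one practice would be an extreme case: 2% of 3,600 is 72, and 60/72 = 83%. The 6 per week is the advice given to treatment patients for three months (Section 3.1.1), not observed behaviour.

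**The case against.** The plan's definition is coherent. A reader might infer that the outcomes are meant to measure new adoption and so measure the wrong thing. Section 1.1 instead defines adoption as any entry during the study period, and (a) and (b) follow it. A reader might also infer bias. Practices are randomised, so prior users are balanced in expectation, and the practice-clustered standard errors are meant to reflect the variation between practices. Nor is a patient with an order but no entries an adopter under (a) or (b); that patient can count only under (c).

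It is also tempting to make patients without prior use the main adoption population. That would drop people who can still respond: a patient with an unused order may start entering, and an existing user may enter more, which is the intensive margin in Section 1.1. It would also measure uptake and A1c in different populations, although the same encouragement is used to study both. Finally, the 2% is an assumed control adoption rate, not a baseline prevalence. Control patients may start during the trial, and Section 1.3 describes ordering as rare.

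All of this stands. It does not explain why a baseline measurement of the outcome that is already being collected is left out of the adjusted model, or what period (c) covers.

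**Conclusion.** The point holds as a loss of efficiency and a gap in definition. Prior use is not handled by eligibility, stratification or adjustment, and (c) is undated. The documents do not support a claim of bias, of noise beyond the stated MDE, or of a wrong adoption definition.

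If half to nearly all of the assumed 2% are prior users, the most that could be gained on (a) is a fall in the MDE from about 9.5 to between 8.4 and 7.0 points. If few of them are, the gain is close to nil. This rests on an unchanged ICC of 0.1, equal practices of 300, 12 practices per arm, a two-sided 5% test and 80% power. For (b) the effect may be larger but cannot be sized from the documents. The change is worth making because it costs almost nothing and bears on the result that determines whether health effects are examined.

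**What to change.** 1. Keep all eligible patients and the Section 1.1 definition of adoption as the main analysis.
2. In Section 4.2, add baseline flowsheet use to the covariates for the practice-level adoption outcomes: any entry and number of entries in the 12 retrospective weeks for (a) and (b), and an active prior order for (c). Order status should be read at the start of administration, since an active order may be older than 12 weeks.
3. Put these terms in a model that can estimate the practice effect. If each doctor works in one practice, the doctor fixed effects listed in Section 4.2 absorb the practice-level treatment, and a covariate added beside them would not help.
4. In Section 3.4, date (c) from the start of the administration period, and say how a patient with an earlier active order is counted.
5. Report (a) to (c) in patients with no prior entry or order as a sensitivity analysis only.

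The cost is a change of wording before analysis, plus order status in the data query if it is not already there. No patient leaves the main analysis.
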